#### 5.2.7.2 Tuberculosis monitoring during the study

At every visit, sites should ensure that the subject has no signs or symptoms of active TB, no recent contact with anyone with active TB, and there is no history of latent (unless diagnosed with documentation of initiation of appropriate treatment) or active TB.

If during the trial a subject is determined to have a:

- **Negative** QFT-G test result, only the annual TB testing is required.
- **Newly positive** QFT-G test result, a chest x-ray has to be performed, and the subject should be referred to a TB specialist. If a TB specialist is not available, the local country guidelines should be followed for further diagnostic work up and anti-TB treatment regimens. If no local guidelines exist for immunocompromised individuals, then USA guidelines may be followed. This should be reported as an AESI. The QFT-G test must be repeated annually.
- For **indeterminate** QFT-G test result, refer to Section [5.2.7.1](#).

QFT-G testing is performed at least annually and in some cases more often, depending on the result. Refer to the Study Plan ([Table 2](#) and [Table 3](#)).

#### 5.2.7.3 Tuberculosis monitoring at Week 156

- **Negative** QFT-G test result: No further testing is required.
- **Newly positive** QFT-G test result at Week 156 or later: Follow prior recommendations for newly positive QFT-G result during study.

- **Newly indeterminate** QTF-G test result (as confirmed on retest unless prior positive QTF-G was documented, along with completed treatment for latent TB): Repeat at Follow-up Visit 1 (8 weeks post-final dose).
  - If negative, no further testing
  - If indeterminate, repeat again at Follow-up Visit 2 (12 weeks post-final dose).

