5. All males (sterilised or non-sterilised) who are sexually active must use a condom (with spermicide where commercially available) for contraception with a woman of child bearing potential from Day 1 until at least 12 weeks after receipt of the final dose of investigational product. It is strongly recommended that female partners of child bearing potential of male subjects use a highly effective method of birth control from [Table 1](#) (other than a barrier method) throughout this period.
6. Females with an intact cervix must have a Pap smear completed and without documented malignancy (eg. no signs of CIN grade III, CIS, or AIS) within 90 days prior to randomization or up until 30 days post-randomization, ie, before IP dosing at V2.  
Subjects with abnormal Pap smear results of atypical squamous cells of undetermined significance (ASC-US), atypical squamous cells where high-grade squamous intraepithelial lesion (HSIL) cannot be ruled out (ASC-H), atypical glandular cells (AGC), or CIN grades I and II (CIN I and II) will be allowed to enter the study [REDACTED].
7. Willing to forego other forms of experimental treatment during the study
8. Meets the following TB criteria:

- (a) **Negative** QuantiFERON®-TB Gold [QFT-G] test result for TB obtained from the study central laboratory at Week 52 of Studies D3461C00004 or D3461C00005

OR

- (b) **Newly positive** QFT-G test result for TB obtained at Week 52 of Studies D3461C00004 or D3461C00005 from the study central laboratory. A chest x-ray must be performed. If the chest x-ray shows no evidence of active TB, and the subject has no symptoms or medical history consistent with active TB, the subject must have a retest. If the retest is positive, the subject must initiate treatment for latent TB within 30 days of randomisation, but prior to the second dose of investigational product administration (Visit 2/Week 4). This should be reported as an AESI.

OR

- (c) **Positive but not newly positive** QFT-G test at Week 52 of Studies D3461C00004 or D3461C00005 from the study central laboratory. The subject must have been diagnosed with latent TB and must have documentation confirming completion of appropriate treatment OR initiate treatment for latent TB within 30 days of randomisation, but prior to the second dose of investigational product administration (Visit 2/Week 4)

OR

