c Interferon-gamma release assay (IGRA) using QFT-G In-Tube Test.

d If a subject has a newly positive QFT-G test at any time during the study or at Week 156, the subject will undergo a chest x-ray to rule out the presence of active TB or other clinically relevant findings. Posterior-anterior and lateral images are required.

- e If subject has a newly indeterminate QFT-G test, it must be repeated every 3 months for the first year and every 6 months thereafter unless it reverts to negative.
- f Investigators should apply local practices for safety monitoring, eg, by serum chemistry tests, in case SOC dose is changed, eg, increased, and/or new DMARD is added.
- g Urine pregnancy test in females of childbearing potential.
- h Only subjects with Hepatitis B core antibody positivity at enrolment of Studies D3461C00004 or D3461C00005. To remain eligible in the LTE study, subject Hepatitis B virus DNA levels must remain below the LLOQ as per the central laboratory.
- i [REDACTED]
- j [REDACTED]
- k [REDACTED]
- l [REDACTED]
- m Monthly tacrolimus trough levels in subjects receiving tacrolimus as standard of care SLE therapy. These subjects must maintain tacrolimus trough levels below the central laboratory upper limit of the therapeutic range based on monthly measurements.
- n Investigational product will be administered as an IV infusion via an infusion pump over a minimum of 30 minutes.
- o If the subject is unwilling to continue with any study visits, including EDV, or is willing to continue with only selected study assessments, at a minimum, these assessments should be completed.
- p No investigational product dosing occurs at Week 156 or EDV.

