#### 5.2.7.1 Tuberculosis results at time of randomisation/Week 52 of the Phase 3 Study D3461C00004 or D3461C00005

- If the QFT-G test result was **negative** and there is no known history of recent exposure to individuals with active TB, the subject may be randomised.
- If the QFT-G test result was **newly positive**, a chest x-ray must be performed. If the chest x-ray shows no evidence of active TB, and the subject has no symptoms or medical history consistent with active TB, the subject must have a retest. If the retest is positive, the subject must start on prophylaxis within 30 days of randomisation, but prior to the second dose (Visit 2/Week 4) in the LTE study. The subject should be referred to a TB specialist. If a TB specialist is not available, the local country guidelines should be followed for further diagnostic work up and anti-TB treatment regimens. If no local guidelines exist for immunocompromised

individuals, then USA guidelines may be followed. This should be reported as an AESI. The QFT-G test must be repeated annually.

- If the QFT-G test was **positive but not newly positive**, the subject must have been diagnosed with latent TB and must have documentation confirming completion of appropriate OR initiate treatment for latent TB within 30 days of randomisation, but prior to the second dose (Visit 2/Week 4).
- If the QFT-G test result was newly indeterminate (as confirmed on retest unless prior positive QFT-G was documented, along with completed treatment for latent TB) or indeterminate but not newly indeterminate, further QFT-G testing will be done according to the Study Plan ([Table 2](#) and [Table 3](#)).

QFT-G testing is performed at least annually and in some cases more often, depending on the result. Refer to the Study Plan ([Table 2](#) and [Table 3](#)).

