### 6.5.5 Tuberculosis

Tuberculosis is a mycobacterial infectious disease generally presenting as cough with systemic symptoms of infection diagnosed by skin test (purified protein derivative), blood test (IGRA), radiographic imaging, body fluid and tissue sampling; presentation may include disseminated or latent disease. An infection may be new (at least conversion of a TB test to positive) or reactivation of dormant disease (new active disease in a previously TB test positive subject without prior evidence of active disease).

- **A bacteriologically confirmed TB** case is a case where a biological specimen is positive by smear microscopy, culture or rapid diagnostic, such as polymerase chain reaction or nucleic acid amplification test (Xpert MTB/RIF).
- **A clinically diagnosed TB** case is a case where the subject does not fulfil the criteria for bacteriological confirmation, but has been diagnosed with active TB by a clinician or other medical practitioner who has decided to give the subject a full course of TB treatment. This definition includes cases diagnosed on the basis of x-ray abnormalities or suggestive histology and extra-pulmonary cases without laboratory confirmation. Clinically diagnosed cases subsequently found to be bacteriologically positive (before or after starting treatment) should be reclassified as bacteriologically confirmed.

Bacteriologically confirmed or clinically diagnosed cases of TB are also classified according to: anatomical site of disease; history of previous treatment; drug resistance; HIV status ([World Health Organization, 2014](#)).

**Latent TB** is a mycobacterial infection without clinical, bacteriological findings, or radiologic findings consistent with active TB and a TB blood test such as an IGRA (QFT-G) or purified protein derivative skin test that is positive both at the time of provisional diagnosis and on repeat assessment.

Subjects identified with latent TB will be assessed by a local TB specialist to confirm the diagnosis and local SOC that will be used in treatment. Once latent TB is confirmed, treatment must be instituted immediately and no investigational product may be administered until treatment of latent TB has begun. Additionally, subjects with newly diagnosed latent TB must agree to complete a locally recommended course of treatment for latent TB to continue to receive investigational product.

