## 6.8 Reporting of adverse events of special interest

Adverse events of special interest will be assessed by the Investigator for severity, relationship to the investigational product, possible aetiologies, and whether the event also meets criteria of an SAE. All AESIs (serious or nonserious) will be recorded on the AE CRF (using a recognised medical term or diagnosis that accurately reflects the event).

The reporting period for AESIs is the period immediately following randomisation through the end of subject participation in the study. Adverse events of special interest that occur prior to randomisation in the LTE study should be reported in Studies D3461C0004 or D3461C00005. Following detection of an AESI (nonserious), reporting is required within 72 hours of knowledge of the event, and for serious AESIs the standard 24-hour timeline for reporting to the appropriate AstraZeneca representative or designee applies. Nonserious non-opportunistic infections will not be captured as AESIs.

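### The tuberculosis AESI rate can mix active TB, repeat-confirmed latent TB and single unconfirmed QFT-G conversions: the protocol's passages on AESI status do not agree, and the SAP has no row that separates them

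*Protocol*

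**What the plan says.** **During the extension.** For a newly positive result, Protocol 5.2.7.2 states: "QFT-G test result, a chest x-ray has to be performed, and the subject should be referred to a TB specialist". The same bullet ends: "This should be reported as an AESI. The QFT-G test must be repeated annually". It contains no retest step. For Week 156, Protocol 5.2.7.3 says: "Follow prior recommendations for newly positive QFT-G result during study". Protocol Table 3, footnote d, asks only for imaging: "the subject will undergo a chest x-ray to rule out the presence of active TB or other clinically relevant findings".

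**At entry.** Where imaging, symptoms and history show no active TB, Protocol 5.2.7.1 says "the subject must have a retest. If the retest is positive, the subject must start on prophylaxis within 30 days of randomisation". Inclusion criterion 8(b) in Protocol 3.1 has the parallel text: "If the retest is positive, the subject must initiate treatment for latent TB within 30 days of randomisation, but prior to the second dose". In both places the instruction to report an AESI comes after the positive-retest sentence.

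**Definition.** Protocol 6.5.5 describes latent TB as an infection without signs of active disease and with a test "that is positive both at the time of provisional diagnosis and on repeat assessment". Earlier in the same section, conversion of a test is accepted as the minimum evidence that an infection is new.

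**Reporting and analysis.** Protocol 6.8 says: "Following detection of an AESI (nonserious), reporting is required within 72 hours of knowledge of the event". SAP 3.1.1 takes AESIs as marked in the eCRF. SAP 4.2.1.1 has one tuberculosis category, with rates by category and preferred term and by time interval. MACE is classified by an adjudication committee; no confirmation step is described for TB.

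**The concern.** Rates of AESIs and SAEs are the primary outcome, and Protocol 8.5.1 wants them examined over time for changes in risk with longer exposure. TB is one of the AESI categories. If a single positive test is enough for an AESI during the extension, the TB rate can include events that do not meet the protocol's own definition of latent TB. A reader of the TB row cannot tell how much of it is active disease, how much is latent TB positive on repeat, and how much is a conversion that was never repeated or not reproduced.

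A second question follows from the analysis groups. Randomised Anifrolumab 300 mg has a larger share of its person-time in the extension than Randomised Placebo. A case definition that loosens at extension entry would therefore affect the two primary groups unequally, and would also produce a step between Year 1 and later years. Whether it does loosen depends on how the feeder studies counted TB events.

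**Working it through.** **1. The passages side by side**

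| Place | Retest mentioned? | AESI instruction |
|---|---|---|
| Inclusion 8(b), Protocol 3.1 | Yes, if no sign of active TB | Directly after the positive-retest sentence |
| Protocol 5.2.7.1 (entry) | Yes, same condition | After the retest, prophylaxis and referral text |
| Protocol 5.2.7.2 (during study) | No | After the x-ray and referral text |
| Protocol 5.2.7.3 (Week 156) | Not for newly positive; yes for newly indeterminate | By reference to the in-study rule |
| Protocol 6.5.5, latent TB | Yes, positive on repeat | Definition only |
| Protocol 6.5.5, general TB | No, conversion is enough | Definition only |

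At entry, the link between retest and AESI status is implied by the order of sentences, not stated.

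**2. Reproducing the plan's person-time**

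Inputs from Protocol 8.2: annual dropout 20% (300 mg) and 30% (placebo and 150 mg); 90% of completers enter; totals 893, 517 and 1343 subject-years. Placebo subjects are re-randomised 1:1 (Protocol 3.6). Feeder arm sizes are not in the documents; back-solving gives 359.9, 359.9 and 89.9, so 360, 360 and 90 are used. Dropout is linear within each year, and 20% per year is used once a subject is on 300 mg.

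- 300 mg: Year 1 = 360 × 0.9 = 324. Extension = 360 × 0.8 × 0.9 × (0.9 + 0.72 + 0.576) = 259.2 × 2.196 = 569.2. Total 893.2.
- Randomised Placebo: Year 1 = 360 × 0.85 = 306. Extension = 360 × 0.7 × 0.9 × 0.5 × (0.85 + 0.595 + 0.4165) = 113.4 × 1.8615 = 211.1. Total 517.1.
- All Anifrolumab: 893.2 + 113.4 × 2.196 + 90 × (0.85 + 0.63 × 2.196) = 1343.2.

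All three totals match the plan. Extension share: 569.2/893.2 = 63.7% against 211.1/517.1 = 40.8%, ratio 1.56.

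**3. Extension tests per group**

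- Annual tests at extension Weeks 52, 104 and 156: 259.2 × (0.8 + 0.64 + 0.512) = 506; 113.4 × (0.7 + 0.49 + 0.343) = 174.
- If every early discontinuer is also tested: 259.2 × 2.44 = 632; 113.4 × 2.19 = 248.

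**4. Unconfirmed events**

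Let q be the probability that a test is newly positive but unconfirmed. The documents give no value; 0.5%, 1% and 2% are assumed, equal in both groups. Each test is treated as a separate chance, a close approximation at small q.

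If the feeder year contributes none (confirmed-only feeder rule), rate per 100 subject-years = 100 × q × tests / total subject-years. With annual tests only:

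| q | 300 mg: events, rate | Placebo: events, rate |
|---|---|---|
| 0.5% | 2.5, 0.28 | 0.9, 0.17 |
| 1% | 5.1, 0.57 | 1.7, 0.34 |
| 2% | 10.1, 1.13 | 3.5, 0.67 |

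The ratio is (506/893)/(174/517) = 1.68 for any q. With early-discontinuation tests it is (632/893)/(248/517) = 1.47.

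If the feeder year also counted single conversions, add one feeder test per subject:

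- Feeder completers only (288 and 252 tests): ratio 1.08, or 1.07 with early-discontinuation tests in the extension.
- All feeder subjects (360 each): ratio 0.94 on either extension count.

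**5. Extension-only tables and time trend**

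At q = 1%, extension-only rates per 100 subject-years are 506/569 = 0.89 against 174/211 = 0.82, or 1.11 against 1.18 with early-discontinuation tests. The groups are nearly equal.

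With single conversions counted in both periods and completers tested, the Year 1 rates are 288/324 = 0.89 and 252/306 = 0.82, the same as in the extension, so there is no step. With a confirmed-only feeder rule the Year 1 contribution is zero, and a step appears in both groups.

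**The case against.** - **The feeder rule is unknown.** A reader might infer that the reporting rule inflates the TB rate on anifrolumab, or makes TB risk appear to rise with exposure. Both readings need a confirmed-only rule throughout the feeder year. The documents support that only in part: the feeder Week 52 assessments serve as the Day 1 assessments (Protocol 4.1), and the entry text mentions a retest. That covers one test in subjects who enter. Events before extension randomisation are reported in the feeder studies, whose rules are not given. This objection stands.
- **The entry text may not gate the AESI.** Protocol 5.2.7.1 and 5.2.7.2 use the same closing AESI wording, and 6.5.5 accepts conversion as evidence of new infection. It is therefore not established that the definition changes at entry, or that the in-study report breaches the protocol. What remains is that the passages can be read differently.
- **Work-up exists.** Protocol 5.2.7.2 provides specialist referral, 6.5.5 has the specialist confirm latent TB, and 5.2.9 has abnormal safety results repeated as clinically indicated. The 72-hour limit governs the first report, not the final record. Even so, the SAP does not say that the outcome of the work-up alters what is counted.
- **The SAP gives some separation.** Preferred-term rows and key subject information may distinguish active disease, latent TB and a positive test. They depend on how sites word the event and do not show whether a positive result was repeated.
- **Unconfirmed is not the same as false.** Protocol 5.2.7 puts the false-negative rate above 12% and warns about immune impairment. A negative repeat may be the wrong result, so dropping unconfirmed conversions from the headline rate would carry its own bias. This also stands, and is why the overall row should stay.

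**Conclusion.** The inconsistency is real, and the SAP leaves it unresolved in a component of the primary outcome. The tuberculosis AESI rate can combine active TB, latent TB positive on repeat and unconfirmed conversions, with no row showing the proportions.

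The size depends on q, which is assumed. At 0.5% to 2%, annual tests alone would add about 0.28 to 1.13 per 100 subject-years on Randomised Anifrolumab 300 mg and 0.17 to 0.67 on Randomised Placebo under a confirmed-only feeder rule. For scale, the precision examples in Protocol 8.2 use 1 and 10 events per 1000 subject-years, that is 0.1 and 1 per 100.

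A between-group artefact is conditional: ratio 1.47 to 1.68 if the feeder year counted confirmed cases only, 0.94 to 1.08 if it counted single conversions. Extension-only tables show almost no gap either way, because both blinded arms share one rule and one schedule. The documents do not establish that the artefact favours or harms either group.

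**What to change.** **Protocol.** Reconcile inclusion criterion 8(b), 5.2.7.1, 5.2.7.2/5.2.7.3 and 6.5.5 so that they say the same thing about when a newly positive QFT-G is an AESI. This concerns AESI status only; no testing, treatment or care rule is proposed, and rapid reporting can stay as it is.

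**SAP.** Keep the overall tuberculosis AESI row. Beneath it add three sub-rows: active TB, latent TB meeting the Protocol 6.5.5 definition, and unconfirmed QFT-G conversion. Put an event with no repeat result on record in the third row. Apply one classification to feeder and extension data, and use it in the overall, extension-only and by-time-interval tables. State in SAP 3.1.1 how the classification is derived and that it may be updated after the first report.

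**Cost.** Wording changes, three sub-rows and a data query per conversion. Some events will be reclassified after first report, and feeder events with no recorded repeat will fall in the unconfirmed row.

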### 5.2.8 Modified Flare Index

A modified SELENA flare index, using the SLEDAI-2K instead of the SELENA SLEDAI, will be completed at the times indicated in the Study Plan (Table 2 and Table 3) to characterise flares as safety events [REDACTED].

The modified flare assessment should be completed by the Investigator or delegated/qualified physician as per protocol schedule of assessments. Assessment of flare should be scored in comparison to the subject's previous visit (ie, over the past 28 days) and should only include findings that, in the opinion of the Investigator, are due to SLE disease activity within that timeframe. Flare will be defined as any 1 criterion present in either the Mild/Moderate Flare or Severe Flare categories. New or worsened manifestations should only be reported for manifestations of SLE.

### 5.2.9 Clinical laboratory tests

All clinical laboratory tests will be performed in a central clinical laboratory at the times indicated in the Study Plan (Table 2, Table 3, and Table 4).

Urine pregnancy tests will be performed at the site using a dipstick. A serum FSH will be performed at randomisation at the central laboratory in newly postmenopausal females with menses absent for  $\geq 1$  year.

Abnormal safety laboratory results should be repeated as clinically indicated, as soon as possible (preferably within 24 to 48 hours). Additional safety samples may be collected if clinically indicated at the discretion of the Investigator.

Every attempt should be made to redraw any missing safety laboratory test samples, even if the subject has received the investigational product.

The Investigator should make an assessment of the available results with regard to clinically relevant abnormalities. The laboratory results should be signed and dated and retained at the site as source data for laboratory variables. For information on how AEs based on laboratory tests should be recorded and reported, see Section 6.6.

In case a subject shows an aspartate aminotransferase (AST) **or** alanine aminotransferase (ALT)  $\geq 3 \times$  upper limit of normal (ULN) **and** total bilirubin (TBL)  $\geq 2 \times$  ULN [REDACTED] 'Actions Required in Cases of Increases in Liver Biochemistry and Evaluation of Hy's Law' for further instructions.

The following laboratory variables in [Table 5](#) will be measured:

**Table 5 Clinical laboratory test**

---

**Randomisation**

[REDACTED]

HbA1c in diabetic subjects only

HBV DNA (testing every 3 months for subjects with HBcAb positivity at enrolment of Studies D3461C00004 or D3461C00005. To remain eligible in the LTE study, subject HBV DNA levels must remain below the LLOQ as per the central laboratory.)

HIV test (only in subjects not tested in Studies D3461C00004 or D3461C00005)

CK

[REDACTED]

Urine protein/creatinine ratio

QFT-G

---

